### **Evaluations Following Randomization**

Creatinine and CBC are collected at 24 ( $\pm$  6 hours). An ECG will be completed at 24 ( $\pm$  6 hours). Subjects randomized to the control arm (best medical management) will have a CTA COW completed at 2-8 hours following randomization. If there is a situation that arises where a subject randomized to the endovascular group does not have a final cerebral angiogram performed, that patient should have a 2-8h CTA to evaluate recanalization. All subjects will undergo a follow-up NCCT scan or brain MRI (including a minimum of diffusion-weighted imaging [DWI], gradient-echo [GRE], FLAIR, and intracranial MR angiography [MRA]) at 24 hours ( $\pm$  6 hours) from the time of randomization. All subjects will have an historical mRS and miFUNCTION scale scores evaluated at 24 hours, 30 days ( $\pm$  7 days) and 90 days ( $\pm$  7 days). All subjects also undergo a NIHSS assessment at 2-8h (at the time of CTA), 24 hours ( $\pm$  6 hours), 48 hours ( $\pm$  6 hours), and 5 days or discharge, whichever comes first, 30 days ( $\pm$  5 days) and 90 days ( $\pm$  7 days). Where the deferral of consent process is approved and in use, all subjects who are enrolled using this process should have the deferral of consent survey completed in the 1-5d window and at 90 days. A mRS will be completed at 30 days ( $\pm$  5 days) and 90 days ( $\pm$  7 days). The Barthel Index will be completed at 30 days ( $\pm$  5 days) and 90 days ( $\pm$  7 days). The EQ-5D will be completed at 30 days ( $\pm$  5 days) and 90 days ( $\pm$  7 days). A cognitive battery using the following subscales will be completed at 90 days ( $\pm$  7 days): Trailmaking A & B, MoCA, Boston Naming test and Sunnybrook hemi-neglect battery. At minimum 90-day outcomes assessments on the mRS, NIHSS and BI should be conducted by an evaluator blind to the acute treatment. It is preferred if all 90-day outcome assessments are conducted by a blinded evaluator.

### **Imaging**

All imaging completed of the brain, NCCT, CTA, Angiogram and MRI will be rendered anonymous and sent to the ESCAPE core lab (Calgary) for central adjudication. Minimally the baseline, 2-8h CTA /Angiogram and the 24-hour imaging should be included. In addition, safety brain scans or other brain imaging within the first 48 hours should be sent to the core imaging lab. Core imaging lab will review all imaging for the acute stroke intervention period. Core imaging requirements are discussed in the MOP. We strongly encourage the use of MR (rather than CT) for the 24-hour brain assessment.

### **Clinical Management of Adverse Experiences**

An adverse event is any untoward medical occurrence associated with the use of a drug in humans, whether or not considered drug related. Adverse events can be any unfavorable and unintended sign (e.g., an abnormal laboratory finding), symptom,

or disease temporarily associated with the use of a drug, without any judgment about causality. Adverse events occur after randomization and are defined as not being present prior to enrolment. For example, a subject with known episodic gouty arthritis of the great toe, who develops an attack of gout is not considered to have suffered an adverse event; the event was known prior to enrolment. A subject who develops a new diagnosis of gout during the study period is judged to have suffered an adverse event. This is reportable as an adverse event even though it is most likely entirely unrelated causally to the study drug, but is instead only associated with study drug use temporally. Adverse events should be managed according to the best current standard of care.

Serious adverse events (SAEs) are those adverse events that are life threatening, require a surgical or medical procedure to prevent disability or death, result in admission to hospital, prolongation of hospitalization or transfer to an ICU, or result in death. A SAE can also be an important medical event that may not result in death, be life-threatening, or require hospitalization, but may jeopardize the subject and may require medical or surgical intervention to prevent one of the outcomes listed in this definition. For example, any new diagnosis of cancer (made after study enrollment) is considered an important medical event. A SAE is also an event that results in a congenital anomaly or birth defect, but this is an unlikely consideration for this trial since all or nearly all participants will not be of reproductive potential. Because our primary safety outcomes for the trial are also serious adverse events by definition, they will be reported dually as SAEs and as outcomes. Serious adverse should be managed according to the best current standard of care.

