|                                | 
according to the current standard of care. Subjects are required to return to clinic on Days 30 & 90 for end-of-study procedures.
  |
| Evaluation Criteria     | 
Safety Analysis: incidence of serious adverse events associated with the treatment protocol. These include:
 
 
a. vessel perforation
 
b. symptomatic ICH
 
c. iatrogenic vessel dissection
 
d. retroperitoneal hematoma
 
e. femoral neuropathy at the groin puncture site
 
f. major extracranial bleeding
 
 
Primary Efficacy Outcome:
 
A shift or one or more categories (proportional odds analysis) on the modified Rankin scale.
 
Key Secondary Outcomes:
 
NIHSS 0-2
 mRS 0-2
 Mortality at 90 days
 EQ-5D (EuroQoL)
 Cognitive outcomes (Trailmaking A, B; MoCA; Boston Naming test; Sunnybrook hemi-spatial neglect battery)
 Barthel Index > 90 (<math>\geq 95</math>)
 Barthel Index shift analysis (ordinal logistic regression)
 miFUNCTION score
 Economic (cost-effectiveness) analysis
 Qualitative evaluation of the waiver/deferral of consent process
 |
| Training Considerations | 
 
1. Optimisation of NCCT scanning protocols and training of CT scanner technicians at each site will be undertaken by the study personnel.
 
2. Training of investigators on the ‘tips and tricks’ of endovascular thrombectomy. Training of the endovascular team (angio suite nurses and technologists) to reduce CT-to-recanalization times.
 
3. Study discipline and rigour on randomization of all patients who might fit these criteria. Given the possibility of the “loss of equipoise” in an active procedural trial, it is critical to get recruitment completed fast and to maintain
 
   |

|                                   |   |
|-----------------------------------|---|
|                                   | study-wide discipline in subject enrolment. Patients must not cross over.   |

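### Under the protocol a fresh attack of a disease known before enrolment is not an adverse event, so non-fatal serious flares of known disease could go unreported as SAEs

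*Protocol*

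**What the plan says.** All the relevant definitions stand in the protocol section Clinical Management of Adverse Experiences.

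- It opens broadly: "An adverse event is any untoward medical occurrence associated with the use of a drug in humans".
- It then narrows: "Adverse events occur after randomization and are defined as not being present prior to enrolment".
- It illustrates the narrowing with gout. A patient with a known episodic form of the disease "who develops an attack of gout is not considered to have suffered an adverse event; the event was known prior to enrolment". The contrast case follows: "A subject who develops a new diagnosis of gout during the study period is judged to have suffered an adverse event".
- It builds the serious category on top of this: "Serious adverse events (SAEs) are those adverse events that are life threatening, require a surgical or medical procedure to prevent disability or death", with admission, prolonged stay, ICU transfer and death as further criteria.
- It adds a second route: "A SAE can also be an important medical event that may not result in death, be life-threatening, or require hospitalization". The only example given for that route is a cancer first diagnosed after enrolment.
- It provides for double reporting of the trial's own safety endpoints: "Because our primary safety outcomes for the trial are also serious adverse events by definition, they will be reported dually as SAEs and as outcomes".

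The section Adverse Event Reporting and Review then sets the flow. Sites enter adverse events on the eCRF, SAEs go to the medical monitor, a safety committee adjudicates safety outcomes and SAEs, and the DSMB reviews the safety profile of the full data set at the end.

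**The concern.** Leaving out a condition that is merely present and stable at baseline is ordinary practice. The gout example goes further. It leaves out a discrete new episode that begins after randomisation, because the underlying diagnosis was already known. Nothing is said about an episode that is worse, more frequent or serious.

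This matters in the expected population. The list of expected patients in the synopsis and under Exclusion Criteria includes people with recent infarction, surgery or bleeding. The section Clinical Management of the Patient anticipates atrial fibrillation, diabetes and borderline renal function. Every participant has a known stroke, and the same section says that those who recover well early carry the highest risk of an early second one. Recurrent stroke is nevertheless not a listed safety outcome, so the SAE channel is its main safety route.

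Safety is a secondary objective, and the per-site share of patients with an SAE is a listed process and quality measure. An event that the site does not record cannot be recovered at the analysis stage, so this is a matter for the protocol and not for a statistical analysis plan.

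A related defect is that the definition speaks of a drug and a study drug, and the reporting section asks about the relationship to an investigational product. The intervention is an endovascular procedure, and control patients receive no study product.

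**Working it through.** The point turns on definitions. There is no stated figure to reproduce, so the check follows one event through the text.

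**Step 1: is the event an adverse event?** Take a patient with known heart failure who decompensates after randomisation and is moved to the ICU. The condition was known and episodic and the attack is new, which is the pattern of the gout example. By that example it is not an adverse event.

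**Step 2: is it an SAE?** The main sentence selects SAEs from among adverse events. An event that fails step 1 is never tested for seriousness, although ICU transfer is one of the criteria.

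**Step 3: does another clause bring it back?**

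| Possible route | What it covers | Reaches this event? |
|---|---|---|
| Important medical event clause | Not expressly limited to new diagnoses, but silent on known disease; its one example is a new diagnosis | Uncertain, left to the site |
| Double reporting of safety outcomes | Under Safety Outcomes: symptomatic intracranial haemorrhage, access-site bleeding, contrast nephropathy, radiation dose, malignant MCA infarction, hemicraniectomy. The synopsis adds perforation, dissection, femoral neuropathy and major extracranial bleeding | No |
| Contrast nephropathy | Creatinine up by 50% or more from the patient's own baseline at 24 h | No; it does catch early renal worsening |
| Process and Quality Outcomes | Aspiration pneumonia, symptomatic DVT/PE | No |
| "Mortality at 90 days" and the mRS | Deaths | Only if fatal |
| Safety committee, medical monitor, DSMB | Events already reported as safety outcomes or SAEs | No, if screened out at the site |

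**Step 4: repeat with other events.** A second infarction or second stroke can be read as a recurrence of known disease (excluded) or as a separate event that was not present at enrolment (included). The text supports either reading, so practice may differ between sites.

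**Step 5: direction and size.** For each arm, let N be the rate of SAEs not linked to known disease and K the rate of SAEs that are flares of known disease, with E for endovascular and C for control. If every K event is omitted:

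- true difference = (N_E − N_C) + (K_E − K_C)
- recorded difference = N_E − N_C

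The recorded incidence is too low by K in each arm. The difference between arms is wrong by K_E − K_C. If flares are background events with K_E = K_C, the absolute difference is unchanged. It shrinks in proportion only if flares carry the same share of the difference as other SAEs. If K_E is below K_C, the recorded difference exceeds the true one. The protocol gives neither N nor K. In a measure that counts patients with any SAE, a patient who also has a recorded SAE is still counted, so the loss in patients is no larger than the loss in events.

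**The case against.** The strongest reply is that the text excludes only what was present before enrolment, that its sole illustration is a mild flare, and that no sensible site would withhold a new infarction. It adds that the synopsis safety analysis centres on acute procedural events such as perforation, haemorrhage and dissection, which the rule barely touches. It also notes that the per-site SAE share is a process measure and not a comparison of arms.

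Much of this stands, and it limits the point. A reader might infer that repeat infarctions certainly go uncounted. The text does not support that, since a site may properly treat one as a new event. A reader might infer that fatal events vanish. They leave at most the SAE tally, because deaths still enter 90-day mortality and the mRS. A reader might also infer that the safety contrast is pulled toward zero. That needs an assumption about how flares divide between arms, for which the protocol offers no basis.

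It can also be said that a broad definition followed by an exclusion is a limitation and not a contradiction, which is fair. The drug wording is likewise secondary. Events are anchored to randomisation, and the Schedule of Assessments plans adverse event review after baseline without distinguishing the arms, so no missed control-arm event follows from it.

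The reply does not remove the rule itself. The protocol states in terms that a new attack of known disease does not count, and it contains no exception for a serious one.

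**Conclusion.** The point holds in this form: the adverse event rule excludes new post-randomisation episodes of known disease, and because SAEs are drawn from adverse events, non-fatal serious recurrences or decompensations could go unreported as SAEs or be reported unevenly between sites. Heart-failure decompensation is the clearest case; recurrent stroke and infarction are ambiguous. The consequence is an understated SAE incidence in what the medical monitor, safety committee and DSMB see, and in the per-site SAE measure.

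Deaths, the listed safety outcomes and qualifying creatinine rises at 24 hours are not affected. No magnitude can be given: the documents contain no rate of pre-existing disease, of flares or of SAEs, and the effect on the difference between arms could go in either direction or be nil. The conclusion assumes that sites apply the gout example as written. Its importance is moderate, and it rests on a stated rule that is simple to correct.

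**What to change.** Replace the rule and the gout example in Clinical Management of Adverse Experiences with a definition along these lines:

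- An adverse event is any untoward occurrence that is new, or that recurs or worsens in severity or frequency, after randomisation in either arm, whether or not it is related to the procedure.
- Only conditions unchanged from baseline are excluded.
- Any event that meets an SAE criterion is reported, whatever the patient's history.
- References to a drug, a study drug or an investigational product, here and in Adverse Event Reporting and Review, are replaced by wording that fits a procedural trial whose control arm receives no study product.

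The cost is a change of protocol wording, a memo to sites and slightly more event forms.

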## Adverse Event Reporting and Review

Adverse events should be reported as they occur on the eCRF. There are no timelines for reporting simple adverse events. Documentation must be supported by an entry in the subject's file. Each event should be described in detail along with start and stop dates, severity, relationship to investigational product as judged by the Investigator, action taken and outcome.

Serious adverse events (SAEs) must be reported within 1 business day of the local investigator's first awareness of its occurrence. SAEs will be reviewed by the trial medical monitor. Because the ESCAPE trial is not a regulatory trial, SAEs do not require reporting to Health Canada, EMEA or other regulatory authorities. Because the adverse event profile of mechanical thrombectomy is well known due to the experience of its use, we do not predict that there will be unexpected adverse events.

**Pregnancies** occurring in study subjects will be treated procedurally as SAEs.

All safety outcomes and serious adverse events will be adjudicated by a designated safety committee comprising a stroke neurologist, and an independent neuro-

radiologist with experience in clinical trials. This adjudication process will determine the classification of the event.

At the end of the study, assuming the study proceeds to completion, the DSMB will be asked again to review the safety profile of the complete study data set and provide an opinion for the record.

Members of the DSMB will be acknowledged publically but will not be considered authors for any manuscripts that arise from this trial. The DSMB members may be involved in academic publications that describe or involve the actions of the DSMB in relation to the trial process. If relevant, this should occur in parallel with or after the publication of the primary manuscript describing the trial. Such a publication should not precede publication of the primary manuscript.

### List of Expected Adverse Events

Expected serious adverse outcome events are the same as the safety outcomes.

### Criteria for Intervention Discontinuation

The intervention is endovascular mechanical thrombolysis/thrombectomy. This procedure will be discontinued if there is an intra-procedural event that warrants stopping. This could include, but is not limited to, intracranial vessel rupture, iatrogenic arterial dissection, failure of the endovascular equipment with breakage of a stent or stent tine, groin or retroperitoneal hematoma, or other acute medical illness that precludes ongoing treatment of the stroke. As a guideline, we strongly recommend stopping the procedure if the time from baseline non-contrast CT is 180 minutes or greater.

Since the intervention is hyperacute only without repetition, it is inferred that the vast majority, if not all patients will have a completed intervention and therefore that the risk of cross-over from the surgical to the medical arm is quite low. We anticipate this could occur due to failure of vascular access, technical failure of angiography equipment, a completely uncooperative subject.

### Statistical Considerations

The primary outcome will be a shift or one or more categories (proportional odds analysis) on the modified Rankin scale determined at 90 days from randomization.

The primary hypothesis is:

HA: Subjects in the intervention arm will have a 1.8-fold greater odds of showing improvement on the mRS at 90 days.

[figure not shown]
The primary analysis will be an intention to treat analysis. It will use an ordinal logistic regression model to derive the common odds of improvement (“shift”) along the mRS scale. The proportional odds assumption will be testing using a Brant test. The analysis will be unadjusted. A secondary analysis using a proportional odds model adjusted for the 6 variables used for minimization (age, sex, NIHSS score, ASPECTS score, occlusion location, intravenous tPA use) will be reported.

A total sample size of 188 ideal patients per group with 90% power is required with alpha at 0.05. The sample size calculation is based upon Whitehead’s power formula. The sample size is estimated without the knowing the distribution of pre-specified confounding variables. We assume no cross-overs. Allowing for losses-to-follow-up (of up to 6%, n=24/400), a total required sample size of 400 ideal patients is anticipated. However, we know that the effect size is highly dependent upon very rapid treatment times and have planned to continue enrolling patients until up to 200 endovascular patients have been treated with a CT-to-first reperfusion time < 90 minutes. We conservatively assume that patients treated later than this time window have show no treatment effect. Currently, in our initial patients we are meeting this quality metric in 60% of our patient population, compared to our desired 80% or greater. Therefore,

- (1) the trial is powered to detect an effect size based upon 400 ideal patients
- (2) the maximum sample size for the trial will be 500 patients to ensure that 200 patients in the endovascular group meet the target treatment times (ie. are ideal patients).

The choice of the shift analysis is based upon empirical evidence that the mRS scale, when categories 5 and 6 are combined, is a true interval scale meaning that any one step increment in the scale is the same; thus, it is unlikely that the proportional odds assumption will be violated and clinical step changes across the scale are meaningful. The proportional odds approach to analysis of the mRS scale is now an accepted methodology in the stroke community and by regulatory agencies. Further, it allows us to include elderly patients (who have a poorer prognosis irrespective of treatment) because a shift from severe to moderate disability will still be recognized as an important outcome. The expected distribution of outcomes is based upon the pooled experience from the literature [SWIFT study, STAR registry, Calgary data, IMS-III study limited to an ESCAPE population, ALIAS part 1 study limited to an ESCAPE population] and a 5% increase in favourable outcomes per mRS category.[Figure] A 5% change across each mRS category is judged to be the minimal clinically important difference.

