| Sample Size Considerations | The study will test the hypothesis that patients undergoing endovascular revascularization will show shift in the distribution of scores on the mRS scale at 90 days, assuming that categories 5 and 6 (bedbound with severe disability, and death) are collapsed, and the effect leads to an assumed common odds ratio of 1.8. The predicted sample size is 500 patients, allowing for potential cross-over and drop-outs.   |
| Randomization              | Randomization will use a minimal sufficient balance algorithm to ensure balance within groups on important predictors of outcome including age, baseline stroke severity, initial arterial lesion location, ASPECTS score and site. We will have suggested time quotas for treatment: CT-to-randomization: 15 minutes; Randomization-to-puncture: 30 minutes; Puncture-to-recanalization: 30 minutes; we will aim to meet this time quotas by ongoing training of the sites and by choosing sites a priori that can meet these targets. |
| Analysis                   | The primary analysis will be an intention to treat analysis. It will use an ordinal logistic regression model to derive the common odds of improvement (“shift”) along the mRS scale. The proportional odds assumption will be testing using a Brant test. The analysis will be adjusted for the 6 variables used for minimization (age, sex, NIHSS score, ASPECTS score, occlusion location, intravenous tPA use).   |
| Consent                    | Waiver/deferral of consent when necessary and where possible according to local IRB approval. Assent or informed consent at other sites. Consent must be obtained within the proposed time targets.   |

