#### **Figure – Projected outcome by mRS category for sample size calculation**

Predicted outcomes by mRS category in the ESCAPE trial, modeled on internal Calgary data, STAR study, IMS-III study. This shows an average 5% improvement in outcomes within each mRS category.

All secondary outcomes will be considered exploratory. Post-hoc analyses will be conducted. A formal statistical analysis plan will be finalized prior to the breaking of the blind, which will outline a details analysis plan for the primary, safety and secondary outcomes in accordance with any protocol changes that may have occurred over the course of the study. This statistical analysis plan will be considered the final analysis plan.

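### The primary ordinal analysis is covariate-adjusted in the synopsis and unadjusted in Statistical Considerations, and its adjustment variables do not match the balancing variables

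*Protocol*

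**What the plan says.** The Analysis row of the protocol synopsis and the section Statistical Considerations describe one analysis in nearly the same terms: intention to treat, ordinal logistic regression, a common odds ratio for shift, and a Brant test of proportionality. They part at the next sentence.

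- Synopsis: "The analysis will be adjusted for the 6 variables used for minimization (age, sex, NIHSS score, ASPECTS score, occlusion location, intravenous tPA use".
- Statistical Considerations: "The analysis will be unadjusted". It continues with "A secondary analysis using a proportional odds model adjusted for the 6 variables used for minimization", giving the same six names.

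The assumed effect is stated in both places without reference to covariates: "the effect leads to an assumed common odds ratio of 1.8" in the synopsis and "Subjects in the intervention arm will have a 1.8-fold greater odds of showing improvement on the mRS at 90 days" in the primary hypothesis. The size is given as: "A total sample size of 188 ideal patients per group with 90% power is required with alpha at 0.05". It comes from Whitehead's formula and is made without knowledge of how the covariates are distributed.

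The text under the projected-outcome figure adds: "A formal statistical analysis plan will be finalized prior to the breaking of the blind". That plan is to be the final one.

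**The concern.** A protocol should have one primary test. Here two are named, and no statement says which section prevails. This is not a detail left open for the statistical analysis plan (SAP), because the protocol has settled it twice, in opposite ways.

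The choice is not cosmetic. With prognostic covariates in the model, the treatment odds ratio is conditional on them and lies further from 1 than the marginal odds ratio from the unadjusted model. The two analyses therefore differ in estimand, in power and, in some trials, in whether the primary result is significant. The assumed 1.8 could be either quantity.

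The adjusted model is itself not cleanly defined. Its covariates are described as those used in allocation, but the allocation text gives another list.

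**Working it through.** **1. The stated sample size.** Inputs from Statistical Considerations and the synopsis: odds ratio 1.8, power 90%, alpha 0.05, scores 5 and 6 merged (six categories), 6% loss to follow-up. Allocation is 1:1 (Study Enrolment Process). Assumptions: two-sided alpha, and equal category proportions, because the outcome figure is not shown.

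n per group = 6(z₀.₉₇₅ + z₀.₉₀)² / [(ln OR)² (1 − Σ p̄ₖ³)]

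- Numerator: 6 × (1.960 + 1.282)² ≈ 63.04
- (ln 1.8)² = 0.5878² = 0.3455
- 1 − 6 × (1/6)³ = 0.9722
- n = 63.04 / (0.3455 × 0.9722) ≈ 187.7, so 188 per group

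Three skewed control distributions give 189 to 191. One-sided alpha gives 153, so the plan's test is two-sided. Then 376 / (1 − 0.06) = 400. The plan's figures reproduce. The formula has no covariate term, so 188 is the size for an unadjusted analysis with a marginal odds ratio of 1.8.

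**2. How far the two models diverge.** The protocol gives no prognostic strength for the covariates, so it is assumed. One normal prognostic score was used, with SD 0.8 or 1.2 on the log-odds scale. As a share of latent variance, SD²/(SD² + π²/3), that is 0.64/3.93 = 16% or 1.44/4.73 = 30%. There were six roughly equal categories, 376 patients split 1:1, and 4,000 trials per row, each fitted both ways.

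| True conditional OR | Score SD | Mean OR, unadjusted / adjusted | Significant, unadjusted / adjusted | Tests disagree | Either significant |
|---|---|---|---|---|---|
| 1.0 | 0.8 | 1.00 / 1.00 | 4.7% / 5.1% | 3.9% | 6.8% |
| 1.0 | 1.2 | 1.00 / 1.00 | 4.6% / 4.6% | 4.9% | 7.1% |
| 1.8 | 0.8 | 1.69 / 1.81 | 82.6% / 90.2% | 10.5% | 91.7% |
| 1.8 | 1.2 | 1.60 / 1.81 | 72.7% / 89.2% | 19.5% | 90.7% |

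The Monte Carlo standard error is at most √(0.195 × 0.805 / 4,000) = 0.6 percentage points in the disagreement column.

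The meaning of 1.8 matters. In shorter runs of 1,000 trials with conditional odds ratios of 2.0 (SD 0.8) and 2.25 (SD 1.2), the unadjusted odds ratios were 1.85 and 1.90, near a marginal 1.8. Power was then 91.4% unadjusted against 95.8% adjusted, and 94.7% against 99.2%. Disagreement fell to 5.2% and 4.9%.

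One limit: allocation in the simulation was not balanced on the score. The trial's balancing algorithm would be expected to bring the two estimates closer and to reduce the null disagreement.

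**3. The covariate lists.**

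| Variable | Adjusted model (synopsis Analysis row; Statistical Considerations) | Synopsis, Randomization row | Study Enrolment Process |
|---|---|---|---|
| Age | yes | yes | yes |
| Sex | yes | no | yes |
| NIHSS / severity | yes | yes | yes |
| ASPECTS | yes | yes | yes |
| Occlusion location | yes | yes | yes |
| Intravenous tPA use | yes | no | no |
| Site | no | yes | yes |

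The adjusted model and the enrolment text each list six variables, but one has intravenous tPA use where the other has site. The Randomization row presents its list as examples, so its omissions weigh less than the clash between the other two.

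**The case against.** The best defence is that the protocol names a tie-breaker: an SAP, due before unblinding, which is to be the final plan. That stands in part. A reader might infer that whoever writes the report is free to pick either p-value. The documents do not support that, because an SAP finalised on time would settle the matter, and it is not shown here. The deferral does not make the protocol consistent, however.

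A second defence is that Statistical Considerations is coherent by itself. The covariate-free Whitehead calculation fits an unadjusted test, and in the simulation each test alone held about 5% error. This also stands: unadjusted is a defensible primary model, and preferring adjustment is an argument about efficiency.

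Two stronger readings should be set aside.

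- A reader might infer that an open-label trial has no blind to break, so that the deadline for the SAP is empty. But the design has blinded outcome evaluation, and the 90-day modified Rankin score is to be rated by an evaluator blind to treatment. The milestone is loosely worded, not meaningless.
- A reader might infer that an unadjusted test leaves the trial short of power. At the stated odds ratio this does not follow. With 500 × 0.94 / 2 = 235 evaluable per arm, the formula in step 1 gives z = √(235 × 0.3455 × 0.9722 / 6) − 1.96 = 3.63 − 1.96 = 1.67, or about 95% power. Whether 1.8 applies to patients treated late is a separate question.

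**Conclusion.** The contradiction is explicit, sits in current text and concerns the test that decides the trial. It should be corrected.

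The sizes are illustrations. If 1.8 is the covariate-conditional odds ratio and the covariates explain roughly 16% to 30% of latent outcome variance, the two tests disagree on significance in about 11% to 19% of trials of 376 patients. If 1.8 is closer to the marginal odds ratio, the figure is about 5%. Under the null it is about 4% to 5%, and choosing the significant test would raise two-sided error to about 7% in the absence of covariate balancing. The existence of the contradiction depends on none of these assumptions.

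The mismatch in covariate lists is a second, linked error: making the adjusted model primary would still leave open whether site and intravenous tPA use belong in it.

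**What to change.** 1. State one primary model in the same words in the synopsis Analysis row and in Statistical Considerations. The preferred choice is the ordinal logistic model adjusted for an explicitly listed set of pre-randomization covariates, with the unadjusted common odds ratio as supportive. Making the unadjusted model primary in both places would also resolve the contradiction and would match the sample size calculation.
2. Reconcile the covariate list with the randomization text. Decide whether site is in or out and whether intravenous tPA use is in or out, and correct the claim that all six variables were used in allocation. If intravenous tPA use stays in, define it by what is recorded before randomization.
3. Say whether the odds ratio of 1.8 is marginal or conditional on the covariates.
4. As a minor clarification, say that the choice is locked before any outcome data are summarised by arm.

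The cost is a few sentences across the synopsis, Study Enrolment Process and Statistical Considerations. If the adjusted model is primary, the reported odds ratio is conditional on the chosen covariates and must be described so. The 188 per group and the total of 400 need no change on this account.
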